11. STATISTICAL PLAN

This section provides the basis for the SAP for the study. The SAP may be revised during the study to accommodate amendments to the clinical study protocol and to make changes to adapt to unexpected issues in study execution and data that may affect the planned analyses. The final SAP will be issued before the first database lock.

Endpoints are listed in Section 4. Analysis variables are listed in Section 5.

11.1. Statistical Hypothesis

No formal statistical testing will be performed for this open-label study.

11.2. Justification of Sample Size

Since this is an open-label single treatment arm study, formal statistical testing is not planned. Therefore, a calculation for patient sample size is not applicable.

Six patients are planned to be enrolled for Part A and 14 pediatric patients are planned to be enrolled for Part B, considering the recruitment constraints in this rare patient population.

11.3. Analysis Sets

11.3.1. Efficacy Analysis Set for Part B

Intent-to Treat

The intent-to-treat (ITT) population is defined as all patients who received at least 1 dose or part of a dose of study drug in Part B.

Modified Intent-to-Treat

The modified ITT (mITT) population is defined as all patients who received at least 1 dose or part of a dose of open-label study drug in Part B and have an evaluable primary efficacy endpoint. The endpoint is considered as evaluable when both of the following conditions are met:

1. Availability of at least 1 measurement value for calculated LDL-C before first dose of study drug (ie, baseline).
2. Availability of at least 1 calculated LDL-C value during the efficacy treatment period and within one of the analysis windows up to week 24. The efficacy treatment period is defined as the time from the first study drug administration up to 35 days after the last study drug administration in Part B.

11.3.2. Safety Analysis Set

Safety Analysis Set: The safety analysis set (SAF) includes all patients who received at least 1 dose or part of a dose of study drug.

Part C Safety Analysis Set: The Part C safety analysis set includes all patients who received at least 1 dose or part of a dose of study drug in Part C.

11.3.3. Pharmacokinetic Analysis Sets

The PK analysis population includes all patients who received any study drug and who had a at least 1 non-missing result for concentration of evinacumab following the first dose of study drug.

The total target analysis population includes all patients who received any study drug and who had a at least 1 non-missing result for concentration of total ANGPTL3 following the first dose of study drug.

11.3.4. Immunogenicity Analysis Sets

The ADA analysis set includes all patients who received any study drug and had at least 1 non-missing ADA result following the first dose of study drug.

Samples positive in the ADA assay may be analyzed in neutralizing antibody assay.

The NAb analysis set includes all patients who received any study drug and who are negative in the ADA assay or with at least 1 non-missing result in the NAb assay following the first dose of the study drug. Patients who are ADA negative are set to negative in the NAb analysis set.

11.4. Statistical Methods

For continuous variables, descriptive statistics will include the following information: the number of patients reflected in the calculation (n), mean, standard deviation, Q1, median, Q3, minimum, and maximum.

For categorical or ordinal data, frequencies and percentages will be displayed for each category.

Data for patients in Part A and patients in Part B will be summarized and listed separately. Similar analyses will be performed for patients in Part A and patients in Part B, respectively, unless otherwise specified.

11.4.1. Patient Disposition

The following will be provided:

- The total number of screened patients: met the inclusion criteria regarding the target indication and signed the ICF
- The total number of patients in each analysis set (eg, ITT, SAF, provided in Section 11.3)
- The total number of patients who discontinued the study, and the reasons for discontinuation
- The total number of patients who prematurely discontinued study treatment in Part B, and the reasons for discontinuation
- The total number of patients who entered Part C
- The total number of patients who prematurely discontinued study treatment in Part C and the reasons for discontinuation
- A listing of patients prematurely discontinued from study treatment, along with reasons for discontinuation

11.4.2. Demography and Baseline Characteristics

Demographic and baseline characteristics will be summarized descriptively for patients in the SAF for Part A, and for patients in the ITT population for Part B.

11.4.3. Efficacy Analyses

11.4.3.1. Primary Efficacy Analysis for Part B

The percent change from baseline in calculated LDL-C at week 24 will be analyzed in the ITT population using a pattern mixture model (PMM) approach as described below (see [Appendix 1](#) for more details).

In the PMM approach, different imputation strategies will be applied to calculated LDL-C values missing during the on-treatment period (ie, within the time period from the first study treatment administration up to the day of last study treatment administration +35 days in Part B) versus calculated LDL-C values missing due to treatment discontinuation after the on-treatment period (ie, after the day of last study treatment administration +35 days in Part B) based on the following assumptions:

- Patients within 35 days of their last study treatment administration in Part B would continue to show benefit from treatment similar to that observed at the scheduled time point. Therefore, calculated LDL-C values missing during the on-treatment period (eg, samples obtained out-side the specified window, no blood sample available although visit was performed, etc.) should be considered “Missing at Random” and imputed based on other observed measurements in the on-treatment period.
- Patients who stopped taking their study treatment in Part B no longer benefited from it after discontinuation, and thus tended to have calculated LDL-C values returning to baseline. Therefore, calculated LDL-C values missing after the on-treatment period should be imputed based on patient’s own baseline value.

Missing data from the ITT population will be imputed 100 times to generate 100 complete data sets, using the SAS MI procedure (using Markov Chain Monte Carlo). The 100 completed datasets of observed and imputed calculated LDL-C data will be used for the primary analysis.

For the percent change from baseline calculated LDL-C endpoint, the 100 complete datasets of observed and imputed calculated LDL-C data at week 24 will be analyzed using the SAS MEANS procedure. The SAS MIANALYZE procedure will be used to generate valid statistical inferences by combining results from the 100 analyses using Rubin’s formulae. Combined estimate for mean at Week 24 will be provided with the standard error (SE) and 95% confidence interval (CI). Formal statistical testing is not planned.

Robustness of this statistical method will be assessed through sensitivity analyses detailed in the SAP, including an ITT analysis and an on-treatment analysis of the percent change in calculated LDL-C from baseline to week 24 using a mixed-effect model with repeated measures (MMRM) approach. All post-baseline data available within the week 1 to week 24 analysis windows will be used and missing data will be accounted for by the MMRM model. The model will include the fixed categorical effect of time point, as well as the continuous fixed covariate of baseline LDL-C value.

11.4.3.2. Secondary Efficacy Analysis for Part B

For the secondary efficacy endpoints (defined in Section 4.1.2), descriptive summaries and analyses will be performed in the ITT population, using values obtained regardless of adherence to study treatment and subsequent therapies (ITT estimand).

For descriptive summaries, percent change, and when appropriate change from baseline, in calculated LDL-C, total-C, non-HDL-C, Apo B, and Lp(a) will be provided at each time point during the 24-week open-label treatment period. All measurements, scheduled or unscheduled, will be assigned to analysis windows defined in the SAP in order to provide an assessment for these time points. Laboratory assessments other than the ones provided by the central laboratory will be excluded. The time profile of each parameter will be plotted with the corresponding SEs.

Multiple types of measurements are planned to be analyzed during differing time points in the trial, specifically continuous measurements expected to have a normal distribution (eg, percent change in calculated LDL-C), continuous measurements expected to have a non-normal distribution [eg, Lp(a)], and binary measurements (eg, proportion of patients with $\geq 50\%$ reduction in calculated LDL-C).

I Continuous endpoints anticipated to have a normal distribution

Continuous secondary efficacy endpoints anticipated to have a normal distribution (ie, lipids other than Lp(a)) will be analyzed using the same PMM approach as for the primary endpoint. In addition, the same sensitivity analyses using MMRM approach as for the primary endpoint will be conducted in the ITT population and mITT population.

II Continuous endpoints anticipated to have a non-normal distribution

Continuous secondary efficacy endpoints anticipated to have a non-normal distribution (ie, Lp(a)), will be analyzed using a robust regression model (ie, ROBUSTREG SAS procedure with M-estimation option) with baseline value as a covariate. Missing values will be addressed using a multiple imputation approach, which will be described in the SAP. The combined means will be provided with respective SE estimates and 95% CI.

III Binary Endpoints

Binary secondary efficacy endpoints will be analyzed with multiple imputation approach for handling of missing values, which will be described in the SAP. Combined proportions will be provided with corresponding 95% CI.

11.4.3.3. Other Efficacy Analyses for Part B

For patients who entered Part C, a combined summary including both the Part B and Part C assessments will be considered, referencing the Part B baseline for variable calculations. Prolonged time between last dose of study treatment in Part B and first dose of study treatment in Part C will need to be taken into consideration when combining longitudinal efficacy data.

11.4.4. Control of Multiplicity

Not applicable.

11.4.5. Safety Analysis

The summary of safety results will be presented for patients in the SAF analysis set. No formal inferential testing will be performed. Summaries will be descriptive in nature.

All safety analyses will be performed using the following common rule:

- The baseline value is defined as the last available value before the first dose of study treatment.

Safety analyses for the Part C treatment period in the Part C safety analysis set of Part A patients will be performed separately for the period pre- versus post-switch to adjusted dose if applicable.

Safety analyses for the combined treatment period of Part B and Part C will be performed in the Part C safety analysis set of Part B patients.

11.4.5.1. Adverse Events

All AEs reported in this study will be coded using the currently available version of the Medical Dictionary for Regulatory Activities (MedDRA®). The verbatim text, the preferred term (PT), and the primary system organ class (SOC) will be listed.

Definitions

For safety variables, the following observation periods are defined:

- The pretreatment period is defined from the day the ICF is signed to the day before the first dose of study treatment.
- The TEAE observation period (Part A or Part B) is defined from the day of the first study treatment administration to the day of the last study treatment administration + 168 days (24 weeks). For patients entering Part C, the TEAE period was truncated at the day before the first study treatment administration in Part C.
- The Part C TEAE observation period is defined from the day of the first study treatment administration in Part C to the day of the last study treatment administration in Part C + 168 days (24 weeks).
- The Part B/Part C combined TEAE observation period is defined from the day of the first study treatment administration in Part B to the day of the last study treatment administration in Part C or to the last study treatment administration in Part B for patients not entering into Part C + 168 days (24 weeks).
- The post-treatment period is defined as the time from the day after the end of the respective TEAE period to the last study visit.

Treatment-emergent adverse events are defined as those events that developed, worsened, or became serious during the respective TEAE period.

Analysis

Adverse event incidence tables will present data by SOC sorted alphabetically and PT sorted by decreasing frequency, and summarize the number (n) and percentage (%) of patients experiencing an AE. Multiple occurrences of the same event in the same patient will be counted only once in the tables. Data conventions for missing or partial AE dates will be addressed in the

SAP. The denominator for computation of percentages is the respective SAF analysis sets (ie, SAF or Part C SAF).

Summaries of TEAEs incidences will include:

- All TEAEs (and patient listing)
- All treatment-emergent SAEs, including patient deaths (and patient listing)
- All TEAEs of special interest
- TEAEs by severity (according to the grading scale outlined in Section 10.2.5), depicting the worse TEAE severity for those patients with multiple occurrences of the same event
- All TEAEs leading to permanent treatment discontinuation (and patient listing)

An AE patient listing will be provided for all patient deaths occurring during the respective TEAE period and the post-treatment period.

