4.8.1. Adverse Events Variables

The period of safety observation starts from the time when the patient gives informed consent and continues into the following periods:

- The PRE-TREATMENT period is defined from the day the ICF is signed to the day before the first dose of study treatment administration.
- The treatment-emergent adverse event (TEAE) period (Part A or Part B) is defined from the day of the first dose of study treatment administration to the day of the last dose of study treatment administration in Part A or Part B respectively + 168 days (24 weeks). For patients entering Part C, the TEAE period is truncated at the day before the first study treatment administration in Part C.
- The Part C TEAE period is defined from the day of the first study treatment administration in Part C to the day of the last study treatment administration in Part C + 168 days (24 weeks).
- The pooled TEAE period is defined below:
 - Part A Patients: defined as the Part C TEAE period.
 - Part B Patients: defined from the day of the first study treatment administration in Part B to the day of the last study treatment administration in Part C + 168 days (24 weeks) or to the last study treatment administration in Part B + 168 days (24 weeks) for patients not entering into Part C.
- The POST-TREATMENT period is defined from the day after the end of the respective TEAE periods to the last study visit.

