4.8.1.1. Adverse Events and Serious Adverse Events

Adverse events (including serious adverse events (SAE), AEs causing permanent treatment discontinuation, deaths, and AEs of special interest) are recorded from the time of signed informed consent until the end of study. All AEs diagnosed by the Investigator will be reported and described.

All AEs will be dictionary coded by “lowest level term (LLT)”, “preferred term (PT)”, “high level term (HLT)”, “high level group term (HLGT)” and associated primary “system organ class (SOC)” using the version of MedDRA in effect at the time of the first database lock.

Adverse Event Observation Period

- Pre-treatment AEs are AEs that developed or worsened or became serious during the pre-treatment period.
- TEAEs are AEs that developed or worsened or became serious during the respective TEAE period.
- Post-treatment AEs are AEs that developed or worsened or became serious during the post-treatment period.

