4.8.1.3. Events Causing Death

The observation periods for patient deaths are per the observation periods defined above.

- Death on-treatment: deaths occurring during the respective TEAE period,
- Death post-treatment: deaths occurring during the post-treatment period.

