Analysis of all treatment emergent serious adverse event(s)

- All Serious TEAEs by primary SOC, HLGT, HLT, and PT
- All Serious TEAEs by primary SOC and PT
- Patient listings of serious TEAEs will be provided in the report appendix
- All Serious TEAEs relationship (related/not related) to evinacumab
- A serious TEAE related to any clinically significant signal will be further characterized as appropriate. The characterization of the clinically significant signal can include Kaplan-Meier curves for time from first dose to first occurrence of selected TEAE, time to resolution, and event duration. Patients without any event will be censored at the end of the respective TEAE period.

Analysis of all treatment-emergent adverse event(s) leading to treatment discontinuation

- All TEAEs leading to permanent treatment discontinuation, by primary SOC, HLGT, HLT, and PT
- All TEAEs leading to permanent treatment discontinuation, by primary SOC and PT
- Patient listings of TEAEs leading to permanent treatment discontinuation will be provided in the report appendix.

- A TEAE leading to permanent treatment discontinuation and related to any clinically significant signal will be further characterized as appropriate. The characterization of the clinically significant signal can include Kaplan-Meier curves for time from first dose to first occurrence of selected TEAE, time to resolution, and event duration. Patients without any event will be censored at the end of the respective TEAE period.

Patient Deaths

The following summaries of deaths will be generated.

- Number (%) of patients who died by study period (TEAE and post-treatment) and reason for death;
- TEAEs leading to death (death as an outcome on the AE CRF page, as reported by the Investigator) by SOC and PT.

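### For a child who enters Part C, the Part A or Part B post-treatment period has no stop at Part C entry, so it overlaps the Part C TEAE period and Part C deaths can carry two labels

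*Protocol*

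**What the plan says.** Protocol 11.4.5.1 sets the TEAE period for Part A or Part B at last dose + 168 days, with an exception for roll-overs: "For patients entering Part C, the TEAE period was truncated at the day before the first study treatment administration in Part C". It then adds: "The post-treatment period is defined as the time from the day after the end of the respective TEAE period to the last study visit". On the next part it says: "The Part C TEAE observation period is defined from the day of the first study treatment administration in Part C", running to the last Part C dose + 168 days.

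SAP 4.8.1 repeats the structure: "The POST-TREATMENT period is defined from the day after the end of the respective TEAE periods to the last study visit".

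The period is then used as follows:

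- SAP 4.8.1.1: "Post-treatment AEs are AEs that developed or worsened or became serious during the post-treatment period".
- SAP 4.8.1.3: "Death post-treatment: deaths occurring during the post-treatment period".
- SAP 5.8.1 plans a table: "Number (%) of patients who died by study period (TEAE and post-treatment) and reason for death".
- Protocol 11.4.5.1 plans a listing: "An AE patient listing will be provided for all patient deaths occurring during the respective TEAE period and the post-treatment period".

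SAP 5.8 presents safety results by study part, so the Part A and Part B death outputs use the Part A and Part B periods.

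**The concern.** The start of the Part A or Part B post-treatment period depends on the truncated TEAE period, but its end does not depend on Part C entry. For a child who rolls over, it therefore covers time during which the child is receiving Part C infusions.

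A programmer who follows the text would give one event two labels: treatment-emergent in the Part C output and post-treatment in the Part A or Part B output. Another programmer could read the last study visit as the last visit of that part and get a different answer. With about 20 children planned (6 in Part A, 14 in Part B) and no control arm, a single death in the wrong column changes how a part-level table reads.

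**Working it through.** **Inputs**

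- Part C visit 1 falls on the day of visit 11 of Part A (day 113) or Part B (day 169): Protocol Tables 1 and 2, and 9.1.1.3 footnote 15.
- Last dose: day 1 in Part A; week 20, day 141, in Part B (Protocol 8.1 and Table 2).
- TEAE tail: 168 days (Protocol 11.4.5.1).
- Last Part C dose: week 48 in Protocol Table 3. The SAP Table 4 follow-up windows imply week 44, because the week-24 follow-up target is day 477 and 477 − 168 = 309 = 44 × 7 + 1. Both are carried through.
- Children entering a CUP or EAP may stop at the Part C end-of-treatment visit, week 48 (Protocol 6.1).

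**Reproducing the plan's durations**

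- Part A + C: 8 + 2 + 16 + 48 + 24 = 98 weeks, as stated.
- Part B + C: 8 + 2 + 24 + 48 + 24 = 106 weeks, as stated.

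**Roll-over child: length of the Part A/B post-treatment period as written**

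Start = Part C Day 1. End = last study visit. Length = end − start + 1.

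| From | Last Part C dose | Part A/B TEAE ends | Post-treatment period | Length |
|---|---|---|---|---|
| Part B | week 48 (day 169 + 336 = 505) | day 168 | day 169 to 505 + 168 = 673 | 505 days |
| Part B | week 44 (day 169 + 308 = 477) | day 168 | day 169 to 477 + 168 = 645 | 477 days |
| Part A | week 48 (day 113 + 336 = 449) | day 112 | day 113 to 449 + 168 = 617 | 505 days |
| Part A | week 44 (day 113 + 308 = 421) | day 112 | day 113 to 421 + 168 = 589 | 477 days |

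The first 337 days (week 48) or 309 days (week 44) run from the first to the last Part C dose. If the last visit is the week-48 end-of-treatment visit, the length is 336 + 1 = 337 days.

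**Comparison with the Part C TEAE period**

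That period starts on the same day and ends at last Part C dose + 168 days. With full follow-up on nominal days, the two periods coincide day for day. With follow-up forgone, the post-treatment period lies wholly inside the Part C TEAE period.

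**Child who does not roll over, for reference**

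- Part B, dosed through week 20: TEAE ends at 141 + 168 = day 309, which is the end-of-study target (±5 days), so 0 to 5 post-treatment days.
- Part A: 1 + 168 = day 169, also the end-of-study target (±3 days), so 0 to 3 days.
- Part B early discontinuer who stays on schedule: with a last dose on day 1, TEAE ends on day 169 and end of study is day 309, so 140 days.

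**Does another rule close the gap?**

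SAP 7.4 switches the post-treatment period off for ongoing patients, but only at the first and second analysis steps. It describes such patients as having neither completed the treatment period concerned nor stopped early. A child who has completed Part B does not clearly fit, and the final analysis is not covered.

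**The case against.** The strongest reply is that the intent is clear. The protocol synopsis says a child entering Part C has no Part A or Part B follow-up period. Protocol 10.1.2 treats follow-up and post-treatment as one period. SAP 4.5 defines the last follow-up visit part by part. On that reading, the last study visit is the last visit of the part concerned. This is probably what was meant, but the definition does not say it. The authors did write explicit roll-over limits for the TEAE period, for concomitant medications (SAP 4.3) and for the Part B laboratory period (SAP 5.8.3). The post-treatment period is the one without such a limit.

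The reply is right about reach. A reader might infer three stronger things that the documents do not support:

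- **That Part C AEs and SAEs would be tabulated as post-treatment.** No such table is specified. The AE and SAE outputs in SAP 5.8.1 are of TEAEs, so for AEs the effect stops at a classification flag.
- **That the tables would confuse on-drug with off-drug events.** TEAE versus post-treatment is not that split, because the TEAE period runs 168 days past the last dose. The SAP also tabulates TEAEs by relationship to evinacumab, and Protocol 10.1.3 requires a narrative for SAEs, including fatal ones.
- **That nearly all Part A/B post-treatment time would be Part C time.** That depends on how many children roll over, which is unknown, and on every other child being dosed through week 20. The 140-day case above shows how far this can fail. No planned output uses post-treatment person-time in any case.

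Nor is any event lost: each remains a Part C TEAE and a pooled TEAE.

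**Conclusion.** The definition is wrong as written, in both documents, for every child who enters Part C. The overlap is nominally 477 to 505 days with full follow-up and about 337 days when follow-up is forgone. These figures assume nominal visit days and same-day entry into Part C; the range reflects the week-44 or week-48 last dose.

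The planned outputs affected are the Part A and Part B death table and the death listing, plus the post-treatment flag on adverse events. The pooled post-treatment period is correct, because it starts only after the pooled TEAE period ends. The documents assume no death rate, so the number of misplaced deaths cannot be estimated, and it may be zero. This is a labelling error with limited reach, worth correcting because the rule is explicit and the correction is small.

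**What to change.** In Protocol 11.4.5.1 and SAP 4.8.1, state two things:

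1. For patients entering Part C, the Part A or Part B post-treatment period, if any, ends the day before the first Part C dose.
2. After Part C entry, post-treatment time is defined only from the day after the end of the Part C or pooled TEAE period to the last study visit.

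Apply the same limit to the post-treatment AE and death definitions (SAP 4.8.1.1 and 4.8.1.3) and to the death table (SAP 5.8.1).

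On the nominal schedule, the Part A or Part B period then has zero days for a roll-over child. Setting an end date is safer than saying no such period exists. Protocol 11.4.3.3 anticipates a prolonged gap before Part C, and if that gap exceeds 168 days there is a genuine interval before Part C whose events still need a label. On nominal dosing, that arises when the first Part C dose comes after day 170 (from Part A) or day 310 (from Part B).

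The cost is a short wording change in each document and one condition in the program that derives the periods. No new data are needed and study conduct does not change.
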